Brief physical examination		X		X ²	X	2. Discharge (32 h post-dose for Treatment Period 1, 2, 4, 5 and 6 in Part A and Treatment Period 1, 3, 4, 5 and 6 in Part C 24 h post-dose for Treatment Period 3 in Part A and Treatment Period 2 Part C)
Medical history (includes substance usage) ³	X					3. Substances: Drugs, Alcohol, tobacco and caffeine
Past and current medical conditions	X					

Procedure	Screening (up to 28 days before Day 1)	Treatment Period 1, 2, 3, 4, 5, 6 Day			Follow-up/Study Discontinuation (7 days post last dose)	Notes ^a
		-1	1	2		
Follicle Stimulating Hormone (FSH) (as needed in women of non-childbearing potential only)	X					
Serum pregnancy test (WOCBP only)	X			X	X	
Urine pregnancy test (WOCBP only)		X				
Human Immunodeficiency Virus (HIV), Hepatitis B and C screening ⁴	X					4. If test otherwise performed within 3 months prior to first dose of study treatment, testing at screening is not required
Tuberculosis (TB) Test	X					
Urine drug screen	X	X				
Alcohol breath test	X	X				
Carbon monoxide breath test	X	X				
Laboratory assessments (haematology, clinical chemistry and urinalysis)	X	X	X ⁵	X ⁵	X	5. Pre-dose (Treatment Period 1 only) and 24 h post-dose Allowable windows in Section 9.4.4
Glomerular filtration rate	X					
C-reactive protein (CRP)	X					

Procedure	Screening (up to 28 days before Day 1)	Treatment Period 1, 2, 3, 4, 5, 6 Day			Follow-up/Study Discontinuation (7 days post last dose)	Notes ^a
		-1	1	2		
12-lead ECG	X ⁶	X	X ⁷	X ⁸	X	6. In triplicate 7. Pre-dose and 2 and 12 h post-dose 8. 24 h post-dose Allowable windows in Section 9.4.3
Vital signs	X	X	X ⁹	X ¹⁰	X	9. Pre-dose and 2 and 12 h post-dose 10. 24 h post-dose Allowable windows in Section 9.4.2
Study treatment			X			
AE review		←=====→			X	
Serious AE (SAE) review	X	←=====→			X	
Concomitant medication review		←=====→			X	
PK blood sample collection			X ¹¹	X ¹¹		11. Time points in Table 2

^a The timing of assessments may be amended in Part C if BID dosing is selected for any of the regimens.

Table 2 Pharmacokinetic Blood Sample Collection Times – Parts A and C

		Part A Treatment Periods 1, 2, 4, 5 and 6 (MR Formulations) Part C Treatment Periods 1, 3, 4, 5 and 6 (MR Formulations)																
Time (h)	Pre-dose	0	2	4	6	8	10	12	14	16	18	20	22	24	26	28	30	32
Dosing		X																
PK sampling	X		X	X	X	X	X	X	X	X	X	X	X	X	X	X	X	X
		Part A: Treatment Period 3 (IR Formulation) Part C: Treatment Period 2 (IR Formulation)																

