Time (h)	Pre-dose	0	0.33	0.66	1	1.5	2	3	4	6	8	10	12	24				
Dosing		X																
PK sampling	X		X	X	X	X	X	X	X	X	X	X	X	X				

^a PK sampling schedule may be amended in Part C if BID dosing is selected for any of the regimens. If BID dosing is employed the number of PK samples may be reduced i.e. some of the samples between 14 and 24 h may not be required. In addition, the 12 h sample will be taken prior to administering the second daily dose.

Table 3 Schedule of Activities for Part B

Procedure	Screening (up to 28 days before Day 1)	Treatment Period 1, 2, 3 Day					Follow-up/Study Discontinuation (7 days post last dose)	Notes
		-1	1	2	3	4		
Informed consent	X							
Inclusion and exclusion criteria ¹	X							1. Recheck clinical status before 1st dose of study medication.
Demography	X							
Demonstrate ability to swallow size 0-00 capsules	X							
Full physical examination including height and weight	X							
Brief physical examination		X				X ²	X	2. Discharge (24 h after the last dose)
Medical history (includes substance usage) ³	X							3. Substances: Drugs, Alcohol, tobacco and caffeine
Past and current medical conditions	X							
FSH (as needed in women of non-childbearing potential only)	X							
Serum pregnancy test (WOCBP only)	X						X	
Urine pregnancy test (WOCBP only)		X						

Procedure	Screening (up to 28 days before Day 1)	Treatment Period 1, 2, 3 Day					Follow-up/Study Discontinuation (7 days post last dose)	Notes
		-1	1	2	3	4		
HIV, Hepatitis B and C screening ⁴	X							4. If test otherwise performed within 3 months prior to first dose of study treatment, testing at screening is not required
Tuberculosis Test	X							
Urine drug screen	X	X						
Alcohol breath test	X	X						
Carbon monoxide breath test	X	X						
Laboratory assessments (haematology, clinical chemistry and urinalysis)	X	X	X ⁵			X ⁶	X	5. Pre-dose 6. 24 h after the last dose Allowable windows in Section 9.4.4
Glomerular filtration rate	X							
CRP	X							
ANA	X					X ⁷		7. 24 h after the last dose

Procedure	Screening (up to 28 days before Day 1)	Treatment Period 1, 2, 3 Day					Follow-up/Study Discontinuation (7 days post last dose)	Notes
		-1	1	2	3	4		
12-lead ECG	X ⁸	X	X ⁹	X ¹⁰	X ⁹	X ¹¹	X	8. In triplicate 9. Pre-dose and 2 and 12 h post-dose 10. Pre-dose 11. 24 h after the last dose Allowable windows in Section 9.4.3 Time points may be subject to change depending on results from Part A

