	
pharmacologic effect of GSK2982772. This may be enhanced in participants taking other immunomodulating drugs or corticosteroids.
 
Clinical data: In the FTiH study, no SAEs were reported.
 
One subject in the FTiH study was diagnosed with herpes zoster 42 days after receiving GSK2982772 80 mg (Treatment Period 2). The blinded investigator considered the AE to be potentially drug-related.
 
One subject from the PsO study experienced an AE of herpes zoster on Study Day 9 (GSK2982772 60 mg BID). The blinded investigator considered the AE to be of moderate severity and not related to study drug.
	
will be excluded from the study.
 
 Participants will be screened for TB, HIV, Hepatitis B and C, and excluded from the study if positive. 
Subject Monitoring:
 
 Participants will be monitored for signs of infection. See Individual Stopping Criteria for atypical or opportunistic infections (Section 8.1.3).
Vaccinations	
No preclinical data.
 
There is a theoretical risk that GSK2982772 could decrease an individual's immune response to vaccines or allow symptoms to develop following vaccination with a live vaccine when administered while on therapy.
	
Subject Selection:
 
 Attenuated or live vaccines should not be administered to participants from 30 days prior to the first dose of GSK2982772, during the study and for 5 half-lives plus 30 days (total 32 days) after GSK2982772 is discontinued. If indicated, non-live vaccines (eg, inactivated influenza vaccines) may be administered while receiving GSK2982772 based on a treating physician assessment of the benefit:risk (eg, risk of theoretical decreased responsiveness). Investigators will be expected to have followed local and/or national guidelines with respect to vaccinations, including against influenza and pneumococcus.

Potential Risk of Clinical Significance	Summary of Data/Rationale for Risk	Mitigation Strategy

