for and magnitude of immunosuppression with this compound is unknown, participants with presence of hepatitis B core antibody (HBcAb) should be excluded. Participants positive for HBsAg and/or positive for anti-HBc antibody (regardless of anti-HBs antibody status) are excluded.

25. An elevated C-reactive protein (CRP) outside the normal reference range.
26. Part B only: A positive anti-nuclear antibody (ANA) outside the normal reference range.
27. Confirmed positive pre-study drug/alcohol screen.
28. Positive human immunodeficiency virus (HIV) antibody test.
29. Regular use of known drugs of abuse, or history of drug or alcohol abuse in the past 5 years.

Other Exclusions

30. Regular alcohol consumption within 6 months prior to the study defined as an average weekly intake of >21 units for males or >14 units for females. One unit is equivalent to 8 g of alcohol: a half-pint (~240 mL) of beer, 1 glass (125 mL) of wine or 1 (25 mL) measure of spirits.
31. Current use or history of regular use of tobacco- or nicotine-containing products within 6 months prior to screening. A carbon monoxide breath test reading of greater than 10 parts per million (ppm).
32. Sensitivity to any of the study treatments, or components thereof, or drug or other allergy that, in the opinion of the investigator or medical monitor, contraindicates participation in the study.
33. Unwilling or unable to swallow multiple size 0-00 capsules as part of study participation.
34. Participants who do not have suitable veins for multiple venepunctures/cannulation as assessed by the investigator at screening.
35. Total cholesterol ≥ 300 mg/dL (≥ 7.77 millimole [mmol]/Liter [L]) or triglycerides ≥ 250 mg/dL (≥ 2.82 mmol/L).
36. Participants who are study site employees, or immediate family members of a study site or sponsor employee.

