12.2. Appendix 2: Clinical Laboratory Tests

- The tests detailed in [Table 8](#) will be performed by The Doctors Laboratory, with the exception of routine urinalysis, urine pregnancy test, urine drug screen, alcohol and carbon monoxide breath tests. These tests will be performed on-site.
- Protocol-specific requirements for inclusion or exclusion of participants are detailed in [Section 6](#) of the protocol.
- Additional tests may be performed at any time during the study as determined necessary by the investigator or required by local regulations.
- All laboratory tests with values that are considered clinically significantly abnormal during participation in the study should be repeated until the values return to normal or baseline. If such values do not return to normal within a period judged reasonable by the Investigator, the etiology should be identified and the sponsor notified.

Table 8 Protocol-Required Safety Laboratory Assessments

Laboratory Assessments	Parameters			
Haematology	Platelet Count	RBC Indices: Mean corpuscular volume (MCV) Mean corpuscular haemoglobin (MCH) Mean corpuscular haemoglobin concentration (MCHC) %Reticulocytes		White blood cell (WBC) count with Differential: Neutrophils Lymphocytes Monocytes Eosinophils Basophils
	Red Blood Cell (RBC) Count			
	Haemoglobin			
	Haematocrit			
Clinical Chemistry ¹	Blood Urea Nitrogen (BUN)	Potassium	Aspartate Aminotransferase (AST)/ Serum Glutamic-Oxaloacetic Transaminase (SGOT)	Total and direct bilirubin (direct only if total is elevated)
	Creatinine	Sodium	Alanine Aminotransferase (ALT)/ Serum Glutamic-Pyruvic Transaminase (SGPT)	Total Protein
	Glucose (fasting)	Calcium	Alkaline phosphatase	Albumin
	Chloride	Cholesterol (Total)	Triglycerides	

Laboratory Assessments	Parameters
Routine Urinalysis	
 • Specific gravity • pH, glucose, protein, blood, ketones, bilirubin, urobilinogen, nitrite, leukocytes by dipstick • Microscopic examination (if blood, protein or leukocytes are abnormal)

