Other Screening Tests	
 • Follicle-stimulating hormone and estradiol (as needed in women of non-childbearing potential only) at screening only • urine drug screen (to include at minimum: amphetamines, barbiturates, cocaine, opiates, cannabinoids and benzodiazepines) • alcohol breath test • carbon monoxide breath test • Urine human chorionic gonadotropin (hCG) pregnancy test (as needed for women of childbearing potential) • Serum hCG pregnancy test (as needed for women of childbearing potential) • Serology (HIV antibody, hepatitis B surface antigen [HBsAg], and hepatitis C virus antibody) at screening only • Tuberculosis test (QuantiFERON) at screening only • C-reactive protein (CRP) at screening only • Anti-nuclear antibody (ANA) in Part B only 
The results of each test must be entered into the CRF.

NOTES :

1. Details of liver chemistry stopping criteria and required actions and follow-up assessments after liver stopping or monitoring event are given in Section 8.1 and Appendix 6 All events of ALT $\geq 3 \times$ upper limit of normal (ULN) and bilirubin $\geq 2 \times$ ULN (>35% direct bilirubin) or ALT $\geq 3 \times$ ULN and international normalized ratio (INR) >1.5, if INR measured, which may indicate severe liver injury (possible Hy's Law), must be reported as an SAE.

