
liver event follow up assessments within 24-72 hrs
 
 Monitor participants weekly until liver chemistries resolve, stabilize or return to within baseline 	
 Anti-nuclear antibody, anti-smooth muscle antibody, Type 1 anti-liver kidney microsomal antibodies, and quantitative total immunoglobulin G (IgG) or gamma globulins. Serum acetaminophen adduct high performance liquid chromatography (HPLC) assay (quantifies potential acetaminophen contribution to liver injury in participants with definite or likely acetaminophen use in the preceding week [James, 2009]. NOTE: not required in China. Liver imaging (ultrasound, magnetic resonance, or computerised tomography) and /or liver biopsy to evaluate liver disease; complete Liver Imaging and/or Liver Biopsy CRF forms.

- Serum bilirubin fractionation should be performed if testing is available. If serum bilirubin fractionation is not immediately available, discontinue study treatment for that subject if ALT \geq 3xULN and bilirubin \geq 2xULN. Additionally, if serum bilirubin fractionation testing is unavailable, record presence of detectable urinary bilirubin on dipstick, indicating direct bilirubin elevations and suggesting liver injury.
- All events of ALT \geq 3xULN and bilirubin \geq 2xULN (>35% direct bilirubin) or ALT \geq 3xULN and INR>1.5, if INR measured, which may indicate severe liver injury (possible 'Hy's Law'), must be reported as an SAE (excluding studies of hepatic impairment or cirrhosis); INR measurement is not required and the threshold value stated will not apply to participants receiving anticoagulants
- Hepatitis A IgM antibody; Hepatitis B surface antigen and Hepatitis B Core Antibody (IgM); Hepatitis C RNA; Cytomegalovirus IgM antibody; Epstein-Barr viral capsid antigen IgM antibody (or if unavailable, obtain heterophile antibody or monospot testing); Hepatitis E IgM antibody

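### Criterion 24 excludes hepatitis B core antibody positives, but the required screening panel lists only HBsAg for hepatitis B, so such a volunteer can reach dosing undetected in Part C

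*Protocol*

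**What the plan says.** Protocol Section 6.2, criterion 24, gives the reason for the rule (how far this compound suppresses immunity is unknown) and states the rule twice: "participants with presence of hepatitis B core antibody (HBcAb) should be excluded", then "Participants positive for HBsAg and/or positive for anti-HBc antibody (regardless of anti-HBs antibody status) are excluded". Anti-HBc positivity therefore excludes even when HBsAg is negative.

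Appendix 2, Table 8, is titled "Protocol-Required Safety Laboratory Assessments". Its serology line reads "Serology (HIV antibody, hepatitis B surface antigen [HBsAg], and hepatitis C virus antibody) at screening only". HBsAg is the only hepatitis B marker in it.

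The SoA rows are generic: "Human Immunodeficiency Virus (HIV), Hepatitis B and C screening" for Parts A and C, and "HIV, Hepatitis B and C screening" for Part B. SAP Appendix 2 repeats them. Note 4 to both rows drops the screening test if one was done within 3 months before first dose. The risk table in Section 3.3.1 is equally general: "Participants will be screened for TB, HIV, Hepatitis B and C, and excluded from the study if positive".

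Hepatitis B core antibody is named as a test only in Protocol Appendix 6, note 3. There it is an IgM assay within the serology that follows a liver stopping event.

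**The concern.** An exclusion can be applied only if screening produces the result it depends on. Criterion 24 needs two hepatitis B results, and the required panel supplies one. The volunteers the anti-HBc clause is there to catch, those who are HBsAg negative and core antibody positive, are the ones the listed panel cannot identify.

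The stake is participant safety and eligibility, not estimation. Waivers are barred in Sections 6 and 9, so dosing such a person would breach eligibility, and without a core antibody result nobody might notice. Table 8 asks for CRF entry of its listed tests, and the inclusion/exclusion deviation summary in SAP Section 4.1 is built from the eCRF page, so a missing anti-HBc result need not surface in either. No pharmacokinetic endpoint or interval is affected.

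**Working it through.** The plan gives no figure to reproduce. The check is whether any screening provision supplies the anti-HBc result.

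1. **Criterion 24 (Section 6.2).** Needs HBsAg and anti-HBc; a positive result on either excludes.
2. **Table 8 (Appendix 2).** Supplies HBsAg, plus HIV and hepatitis C antibody. No anti-HBc.
3. **SoA hepatitis rows, their SAP copy, and the Section 3.3.1 risk table.** Name no marker. Section 9.4.4 refers to Appendix 2 for the definition of the required laboratory assessments, so the generic wording leads back to Table 8.
4. **SoA note 4.** Does not say which markers an earlier test must have covered. An HBsAg result within 3 months could be read as enough.
5. **Appendix 6, note 3.** Core IgM after a liver event. This comes after dosing and cannot serve eligibility.
6. **Other eligibility checks.** Criterion 13 (ALT), criterion 14 (bilirubin) and criterion 15 (known liver disease) do not detect an anti-HBc-positive volunteer with normal liver tests and no known history.

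No listed screening test yields the second result. This looks like an omission, because the other laboratory-based exclusions do have a listed test: ALT, bilirubin, lipids, tuberculosis, CRP, ANA in Part B, HIV, hepatitis C, drug screen and carbon monoxide are in Table 8, and glomerular filtration rate is in the SoA.

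**Illustrative size.** Let p be the anti-HBc prevalence among otherwise eligible HBsAg-negative volunteers. The documents do not give it; 1% to 5% is assumed. With n independent participants, no anti-HBc test done and nobody caught by another route, P(at least one) = 1 − (1 − p)^n.

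| n | Source | p = 1% | p = 5% |
|---|---|---|---|
| 16 | Part C planned enrolment, Section 5.2 | 1 − 0.99^16 = 1 − 0.851 = 15% | 1 − 0.95^16 = 1 − 0.440 = 56% |
| 24 | Part C maximum dosed, Section 5.2 | 1 − 0.99^24 = 1 − 0.786 = 21% | 1 − 0.95^24 = 1 − 0.292 = 71% |

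Parts A and B are left out because Section 3.1 describes them as complete.

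**The case against.** The best defence is that Table 8 is a minimum, not a limit. Appendix 2 refers the reader to Section 6 for inclusion and exclusion requirements and lets the investigator add tests. Section 9 requires screening to confirm every eligibility criterion, so an investigator without an anti-HBc result cannot properly sign off criterion 24. The SoA wording is broad enough to include anti-HBc. Table 8 is not exhaustive elsewhere either: criterion 9 accepts a T-spot test that Table 8 does not list. Section 9.4.4 also cites a laboratory manual, not among the documents, which might specify the assay.

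This stands against one tempting inference: that such volunteers will pass screening and be dosed, or that the exclusion is simply not enforced. The documents support only that they can pass if the Table 8 panel is run as written or note 4 is read loosely. It does not remove the mismatch, since permission to add a test is not a requirement to do it, and the duty to confirm criterion 24 calls for a result that no required test supplies.

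Two other extensions should be resisted. A reader might count all 42 planned participants (16 + 10 + 16), but a wording change cannot affect the completed Parts A and B. A reader might also infer that a later ALT rise could not be attributed. Appendix 6 partly meets that: ALT at or above 3 times the upper limit of normal triggers hepatitis serology with HBsAg, which can be compared with the negative screening result, plus core IgM. Part C exposure is also brief: single doses at least 7 days apart, with at most one twice-daily dosing day planned, of a drug with a half-life of about 2 to 3 hours.

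**Conclusion.** The inconsistency is established from the text: the anti-HBc part of criterion 24 cannot be applied from the required screening tests. Whether anyone is dosed contrary to the criterion depends on what the site actually orders, which the documents do not show. The number affected cannot be estimated from them either. The 15% to 56% chance of at least one such participant among 16 rests wholly on the assumed 1% to 5% prevalence and on no anti-HBc testing and no other route of detection; it shows scale and is not a forecast. This is an internal inconsistency worth correcting because it concerns a stated safety exclusion and the repair is small.

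**What to change.** Reconcile criterion 24, the Table 8 serology entry and the SoA hepatitis rows so that the listed screening tests cover every marker the criterion uses:

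- Add hepatitis B core antibody to the Table 8 serology line. Criterion 24 names no assay class, so the sponsor should state which one it intends.
- Name the same markers in the SoA hepatitis rows and in their copy in SAP Appendix 2.
- Amend note 4 so that earlier testing waives screening only when results for all listed markers are on file.

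The cost is protocol wording, one more assay on the existing screening sample, and possibly a few more screen failures. No new eligibility rule is introduced.

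The treatment labels in SAP Section 5.1 suggest that Part C dosing had taken place when that plan was written. For anyone already dosed, new wording does not help; the sponsor can only check whether a core antibody result is on file.

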6.3. Lifestyle Restrictions

6.3.1. Meals and Dietary Restrictions

- Refrain from consumption of red wine, Seville oranges, grapefruit or grapefruit juice, pomelos, exotic citrus fruits, grapefruit hybrids, or fruit juices from Seville oranges and grapefruit derivatives for 24 hours before admission to each study period until after collection of the final PK sample in that period.
- Refrain from consumption of poppy seeds for 48 hours before screening, and from 48 hours before admission to each study period until after collection of the final PK sample in that period.

- For fasted dosing, no water is allowed from 1 hour before dosing until 1 hour after dosing with the exception of the 240 mL water provided with each dose. Water is allowed ad libitum at all other times.
- For fasted dosing, participants will be provided with a light snack on the evening before dosing and will be required to fast from all food and drink (except water) for a minimum of 10 hours before dosing until approximately 4 hours after dosing. Lunch will be provided approximately 4 hours after dosing, an evening meal will be provided approximately 10 hours after dosing and an evening snack will be provided approximately 14 hours after dosing.

If BID dosing in the fasted state is selected for Part B or Part C Period 6, participants will be dosed in the evening approximately 12 hours after the morning dose. Meals will be provide as described above (i.e., no food will be permitted 2 hours before and 2 hours after dosing).

- For dosing after a high fat breakfast (Part A and optionally Part C) or a standard breakfast (Parts B and C), participants will be provided with a light snack and will fast from all food and drink (except water) until the following morning, when they will be provided with the appropriate breakfast. The breakfast should be consumed over a maximum period of 25 min, with dosing occurring 30 min after the start of breakfast. Participants should be encouraged to eat their meal evenly over the 25 min period. It is acknowledged that some participants will take less time to eat, but dosing should still occur 30 min after the start of breakfast. Lunch will be provided approximately 4 hours after dosing, an evening meal will be provided approximately 10 hours after dosing and an evening snack will be provided approximately 14 hours after dosing.

If BID dosing administered with food is selected for Part B or Part C Period 6, participants will be dosed in the evening following a standard evening meal. Meals will be provided as described above (with evening dosing approximately 30 minutes after the start of the evening meal).

- If dosing before a standard meal is selected in Part C, participants will be provided with a light snack on the evening before dosing and will be required to fast from all food and drink (except water) for a minimum of 10 hours before dosing. No water is allowed from 1 hour before dosing until 1 hour after dosing, with the exception of the 240 mL water provided with each dose. Water will be allowed ad libitum after dosing or after administration of the standard breakfast, whichever is sooner. A standard breakfast will be provided either 30 or 60 minutes after dosing. Lunch will be provided approximately 4 hours after dosing, an evening meal will be provided approximately 10 hours after dosing and an evening snack will be provided approximately 14 hours after dosing.
- If drug administration in Part B is in the fasted stated, then on Day 2 when PK samples are not being collected, meals will be provided at appropriate times, i.e., a standard breakfast at approximately 2 hours post-morning dose, lunch at approximately 4 hours post-morning dose, dinner at approximately 10 hours post-morning dose and an evening snack at approximately 14 hours post-morning dose.

- If drug administration in Part B is in the fed state, then on Day 2 when PK samples are not being collected, meals will be provided at appropriate times, i.e., a standard breakfast 30 mins prior to the morning dose, lunch at approximately 4 hours post-morning dose, dinner at approximately 10 hours post-morning dose and an evening snack at approximately 14 hours post-morning dose.
- During each dosing session, participants will abstain from ingesting caffeine- or xanthine-containing products (eg, coffee, tea, cola drinks, and chocolate) for 24 hours before admission until after collection of the final PK sample in that period.
- Participants will abstain from alcohol for 24 hours before screening. During each dosing session, participants will abstain from alcohol from 24 hours before admission until after collection of the final PK sample in that period.
- Current smokers or users of other tobacco products will not be enrolled in this study.

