7.1.2. Treatments Administered - Part B

Regimen	G	H	I
Study Treatment Name:	GSK2982772	GSK2982772	GSK2982772
Dosage formulation:	Prototype MR Minitablet in Capsule Formulation X	Prototype MR Minitablet in Capsule Formulation X	Prototype MR Minitablet in Capsule Formulation X
Unit dose strength(s)/ Daily Dosage level(s)^a:	15 or 30 mg / 30 mg	30 or 60 mg / 60 mg	60 mg / 240 mg
Route of Administration	Oral with 240 mL water		
Dosing instructions:	1 x 30 mg capsule in the morning of Days 1 to 3 or 1 x 15 mg capsule in the morning and evening of Days 1 to 3; dosing will be 12 hours apart Fasted or Fed (non-high fat meal)	1 x 60 mg capsule in the morning of Days 1 to 3 or 1 x 30 mg capsule in the morning and evening of Days 1 to 3; dosing will be 12 hours apart Fasted or Fed (non-high fat meal)	4 x 60 mg capsule in the morning of Days 1 to 3 or 2 x 60 mg capsule in the morning and evening of Days 1 to 3; dosing will be 12 hours apart Fasted or Fed (non-high fat meal)
Packaging and Labelling	Study Treatment will be provided in a 85 cc HDPE white bottle. Each HDPE bottle will be labelled as required per country requirement.		
Manufacturer	Quotient		

Formulation X is the formulation selected from Part A

^a Daily dosage levels are the anticipated dose levels for Part B; but may be subject to change depending on the results from Part A.

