9.5. Pharmacokinetics

- Blood samples of approximately 2 mL will be collected for measurement of plasma concentrations of GSK2982772 as specified in the SoA (see Section 2). Instructions for the collection and handling of biological samples will be provided by the sponsor. The actual date and time (24-hour clock time) of each sample will be recorded.
- Processing, storage and shipping procedures are provided in the Study Reference Manual (SRM) or equivalent.
- The acceptable deviations from the nominal post-dose blood sampling times are as follows:
 - The pre-dose blood sample will be taken ≤ 1 hour before dosing.
 - Post-dose samples will be taken within ± 10 minutes of the nominal post-dose sampling time
- Samples will be used to evaluate the PK of GSK2982772. Samples collected for analyses of GSK2982772 plasma concentration may also be used to evaluate safety aspects related to concerns arising during or after the study.
- Genetic analyses will not be performed on these plasma samples. Participant confidentiality will be maintained.

Plasma analysis will be performed under the control of Platform Technology & Science (PTS), In Vitro/In Vivo Translation (IVIVT) and Third Party Resourcing (TPR), GSK. Concentrations of GSK2982772 will be determined in plasma using the current approved bioanalytical methodology. Raw data will be archived at the Bioanalytical site as detailed in the SRM or equivalent.

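### In the optional fed BID branch, the meal timetable puts dose 2 at about 10.5 h, although the 12 h PK sample is meant to precede dose 2

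*Protocol*

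**What the plan says.** Protocol Section 6.3.1 times fed-day meals from the morning dose: lunch at about 4 h, then "an evening meal will be provided approximately 10 hours after dosing and an evening snack will be provided approximately 14 hours after dosing". Where BID dosing with food is chosen for Part B or Part C Period 6, the same section says: "Meals will be provided as described above (with evening dosing approximately 30 minutes after the start of the evening meal". It gives no other evening-meal time for fed BID. The Part B fed Day 2 bullet repeats the timetable: "a standard breakfast 30 mins prior to the morning dose, lunch at approximately 4 hours post-morning dose, dinner at approximately 10 hours" after the morning dose.

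Other instructions assume 12 h:

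- The Table 2 footnote (Part C) and Table 4 footnote b (Part B) in Protocol Section 2 both state: "In addition, the 12 h sample will be taken prior to administering the second daily dose". SAP Section 10.2.1 repeats both.
- The Part B dosing table in Protocol Section 7.1.2 states: "dosing will be 12 hours apart Fasted or Fed (non-high fat meal".
- The fasted BID paragraph of Section 6.3.1 states: "participants will be dosed in the evening approximately 12 hours after the morning dose".

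For Part C, Regimen O in Section 7.1.3 provides only for morning and evening dosing on Day 1. It gives no interval in hours.

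**The concern.** A site running fed BID could not follow the meal paragraph and the sampling footnote together. It would have to move the meal without instruction, separate the dose from the meal, or sample after dose 2.

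The 12 h sample is what separates the two doses. In Part C, Protocol Section 4 lists AUC(0-12), C12h and Cmax:C12h as the endpoints added if BID is used. If dose 2 has already been given, C12h is no longer the trough of the morning dose and AUC(0-12) includes early absorption from the second. Sampling just before dose 2 instead would give a value at 10.5 h, whereas SAP Section 10.6.4.1 defines C12h as the concentration observed at 12 hours.

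**Working it through.** **Inputs**

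- Evening meal, fed days: about 10 h after the morning dose (Protocol 6.3.1).
- Evening dose, fed BID: about 0.5 h after the meal starts (Protocol 6.3.1).
- Lunch at about 4 h and evening snack at about 14 h (Protocol 6.3.1).
- Interval stated for Part B: 12 h (Protocol 7.1.2).
- PK sampling window: plus or minus "10 minutes of the nominal post-dose sampling time" (Protocol 9.5).

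**Control: the fasted BID paragraph.** The meal is at 10 h, dose 2 at 12 h and the snack at 14 h. The gaps are 12 − 10 = 2 h and 14 − 12 = 2 h, which match the food-free 2 h before and after dosing stated there. The stated 12 h is reproduced, and the reference back to the earlier meal description evidently carries the clock times with it.

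**Fed BID**

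1. Dose 2 = 10 h + 0.5 h = 10.5 h. The stated 12 h is not reproduced.
2. Shortfall = 12 h − 10.5 h = 1.5 h = 90 min, which is 90 / 10 = 9 times the sampling tolerance.
3. An in-window 12 h sample is taken between 11 h 50 min and 12 h 10 min. Subtracting 10 h 30 min puts it 80 to 100 min after dose 2.
4. AUC(0-12) then includes the first 12 − 10.5 = 1.5 h after dose 2.

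**Part B only**

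5. Time from dose 2 to the next morning dose = 24 h − 10.5 h = 13.5 h, so the intervals are 10.5 h and 13.5 h instead of 12 h and 12 h.
6. AUC(12-24) would cover 1.5 h to 13.5 h after dose 2.

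The last two steps do not carry over to Part C. Regimen O is dosed on Day 1 only, so no second interval exists. AUC(12-24) is a listed endpoint for Part B alone (Protocol Section 4; SAP 8.2.1.2), although a plotting sentence in Protocol 10.4.1 covering both parts mentions it.

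**Meal time that restores 12 h.** 12 h − 0.5 h = 11.5 h. Lunch to evening meal becomes 11.5 − 4 = 7.5 h instead of 10 − 4 = 6 h. The 14 h snack can stay, 2 h after dose 2.

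**The case against.** The strongest reply is that the fed BID paragraph never states 10.5 h. That time is inferred, while the explicit rules point to 12 h, so a sensible site would serve the meal later. The protocol is also flexible. Section 7.2 allows some alteration of the dosing schedule, a Table 1 footnote lets assessment times change under BID in Part C, and the Table 2 footnote adds: "PK sampling schedule may be amended in Part C if BID dosing is selected for any of the regimens". Regimen O is a placeholder, to be settled at a documented interim review.

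Much of this limits the practical risk, but it does not make the text consistent. Section 7.2 refers to the dose plan in Sections 5.1 and 5.5. The two footnotes move assessments and samples, not meals or doses, and the Table 2 footnote still places the 12 h sample before dose 2. The interim review is described as setting dose, prandial state and QD or BID, with no mention of meal times. A difference of 90 minutes is also too large to attribute to approximate times.

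The objection on scope stands. Protocol Section 3.1 says Parts A and B were complete when Part C was added, so the conflict with the Part B dosing table was no longer live. The Part C food-effect and dose models (SAP 8.2.5.3) use neither AUC(0-12) nor C12h.

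A reader might go further and infer that reported results are distorted. The documents do not support that. In SAP Section 5.1 the Part C Period 6 display label is a 240 mg delayed-fed, high-fat regimen with no mention of BID, and the Part B labels do not state a dosing frequency. Nor are the primary Part C comparisons touched, although AUC(0-12) and C12h are among their endpoints: Periods 1 and 2 are single fasted morning doses.

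**Conclusion.** The inconsistency is real and minor. Read at its nominal times, Section 6.3.1 puts dose 2 of fed BID about 1.5 h too early for the Table 2 footnote to be met. For Part B, already complete, it also contradicts the Table 4 footnote and the 12 h interval in Section 7.1.2. In Part C it conflicts with the sampling footnote only. It would be tempting to say that Part C breaks a stated 12 h dosing interval, but Regimen O states none.

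The live scope is Part C Period 6, and only if fed BID is chosen, the meal rule is followed and sampling stays at 12 h. C12h, Cmax:C12h and AUC(0-12) would then be contaminated by dose 2, in descriptive summaries. The size can be given only as timing (80 to 100 min after dose 2). The documents do not allow a bias to be calculated, and none is claimed. The branch was apparently not used.

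**What to change.** In Protocol Section 6.3.1, state that for fed BID dosing the evening meal starts about 11.5 h after the morning dose, the 12 h PK sample is taken immediately before dosing, and dose 2 is given at about 12 h. In Section 7.1.3, add to the BID option of Regimen O that the doses are approximately 12 hours apart. Align the Part B fed Day 2 bullet for consistency only, since that part is finished. The SAP needs no change: its schedule already places the 12 h sample before the second dose.

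The cost is wording in one meal paragraph, one bullet and one table cell. In conduct, evening meals would fall at different times on QD and fed BID days, and participants would wait 7.5 h instead of 6 h between lunch and the evening meal.
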